1.2.3 Tertiary objectives and endpoints

1.3 Design

This is a multi-centre, dose escalation, Phase I trial in two parts.

In Part 1 each patient cohort included up to six evaluable patients following a rolling six dose escalation scheme (Skolnik A.M. *et al.*, 2008) of AZD3965 until a recommended Phase II dose (RP2D) and/or the maximum tolerated dose (MTD) was defined.

42 patients with advanced solid tumours or Lymphoma were entered into Part 1. The final number depended on the number of dose escalations required to reach MTD or the tolerated dose at which monocarboxylate transporter 1 (MCT1) was inhibited. A RP2D was proposed from the safety and pharmacokinetic (PK) results from Part 1.

All patients in Part 2 will be treated at this RP2D to further explore the tolerability of this dose and schedule and to explore proof of principle of MCT1 inhibition in tumour types that were shown to express high MCT1 and low monocarboxylate transporter 4 (MCT4) or in which AZD3965 showed some effect pre-clinically.

In Part 2 there will be up to 20 evaluable patients entered with relapsed or refractory diffuse large B cell Lymphoma (DLBCL) and Burkitt Lymphoma (BL).

1.4 Administration schedule

AZD3965 is available as 5, 10, 20 and 30 mg capsules and patients will take their dose orally once or twice every day (in the absence of toxicity).

One treatment cycle will consist of 28 days (with Cycle 1 including an additional dosing day at Day -7⁴ for Part 1 of the trial only).

In the Part 1 dose escalation, up to six evaluable patients were treated at each dose level with a dose on Day -7 followed by continuous daily dosing starting on Day 1 (in the absence of toxicity after the Day -7 dosing).

The starting dose was 5 mg once daily and the next total daily dose level was 10 mg.

Pharmacokinetic (PK) assessments were performed to assess the half-life and potential accumulation of the drug in order to inform whether dosing for future cohorts should be once or twice daily.

The total daily dose was doubled in successive cohorts until a Grade 2 highly probable or probably related adverse drug reaction was reported according to the National Cancer Institute Common Terminology Criteria for Adverse Events (NCI CTCAE) Version 4.02. Subsequent dose increases between cohorts were up to a maximum of 50% (to the nearest 5 mg) driven by reported safety, PK and pharmacodynamic (PD) data. However, an upper limit on dose escalation was set using PK data (see Section 2.2.9). If continuous daily dosing is not tolerated at levels that inhibit MCT1 then intermittent schedules will be explored.

Up to six evaluable patients were treated at each dose level. At least one male patient was treated in each cohort If a dose limiting toxicity (DLT) was observed then the cohort was expanded to six patients. If a second DLT was reported no further dose escalation was performed and a total daily dose level below was expanded to six patients to identify the MTD.

An interval of 14 days (from Day -7 (7 days prior to Day 1) was observed between the recruitment of the first and second patients in a cohort but the subsequent patients were treated in parallel. Twenty-eight days (from Day 1) of data (safety, PK and PD) was available for a minimum of three patients in a cohort in order to make the decision to dose escalate.

In both Parts 1 and 2, AZD3965 will be administered as continuous daily dosing in 28 day cycles for up to six cycles. If the patient is benefitting from the treatment, a further six cycles may be administered after discussions between the Investigator and the Sponsor, Cancer Research UK's Centre for Drug Development (CRUK CDD). In the case of toxicity, treatment will be interrupted and then resumed when all toxicities have returned to Grade 1 or baseline. Intermittent dosing schedules may be explored based on observed toxicities.

In Part 2 all patients will be treated at the RP2D determined in Part 1. There will be no Day -7 dose in Part 2. All patients in Part 2 will be treated at the RP2D as continuous daily dosing in 28 day cycles for up to six cycles starting on Day 1. If the patient has not progressed after six cycles, further cycles may be given after discussion between the Investigator and the CDD (see Section 5.7).

An interval of 14 days (from Cycle 1 Day 1) must be observed between the recruitment of the first and second patient in the expansion cohort but subsequent patients can be treated in parallel. Data must be available (safety and PK) for a minimum of three evaluable patients in order to make any decision to change the Part 2 dose (RP2D). Any changes to the Part 2 dose (RP2D) will be for safety reasons and to decrease the total daily dose only.

1.5 Treatment group

42 patients with advanced solid tumours were entered into Part 1, and up to 20 evaluable patients with DLBCL and BL will be entered into Part 2. The final total patient numbers will depend on the number of dose levels explored in Part 1 and the number of patients recruited to Part 2.

1.6 Trial timelines

It was expected that the trial would have a minimum duration of 36 months in Part 1 and will have a minimum duration of 24 months in Part 2.

⁴ Day -7 dosing may be performed on Day -8 to Day -6. See Section Error! Reference source not found.

2 INTRODUCTION

2.1 Background

[figure not shown]
2.1.1 Monocarboxylate transporter 1 (MCT1) and Cancer

AZD3965 is a first in class, potent and selective MCT1 inhibitor originally developed by AstraZeneca (AZ). AZD3965 targets the increased dependency on the glycolytic pathway for adenosine tri-phosphate (ATP) generation present in many tumour types, by preventing the excess lactic acid from being exported via MCT1 thereby resulting in acidosis and cell death. As such AZD3965 represents a novel potential mechanism of action to target tumour cells and an opportunity of bringing a new class of agents into the clinic.

The tumour cell population is heterogeneous as tumours contain both oxygenated and hypoxic regions (Sonveaux et al., 2008). Normal differentiated cells rely primarily on mitochondrial oxidative phosphorylation to generate the energy needed for cellular processes. In contrast most tumour cells have an increased dependency on the glycolytic pathway for ATP generation either via aerobic glycolysis (Warburg effect) or anaerobic glycolysis (Pasteur effect) as a consequence of tumour hypoxia. This glycolytic phenotype offers a number of survival advantages to the tumour as it allows the cell to meet its energetic and anabolic requirements, survive in fluctuating oxygen tensions and to generate glycolytic intermediates that can be used to fuel additional biosynthetic pathways. Key tumour associated pathways drive this phenotype including Myc, p53, Ras and hypoxia leading to the upregulation of a number of glycolytic enzymes and glucose/lactate transporters in tumours.

Therefore, as a result of the preferential utilisation of the glycolytic pathway and lactate production by tumour cells, the primary hypothesis is that inhibiting MCTs will prevent lactate transport out of cells, thereby generating both feedback inhibition of glycolysis and a pH imbalance that can lead to cytostatic or cytotoxic effects.

A secondary hypothesis, that is less well developed but supported by the expression profile of enzymes and transporters in tumour tissues, proposes that normoxic tumour-associated stromal cells, or normoxic tumour cells, can take up lactate via MCTs and use this as an energy source by converting it back to pyruvate. In this model, inhibition of lactate uptake would increase the glucose dependency of the normoxic cells and therefore deprive hypoxic or Warburg tumour cells of glucose (Sonveaux et al., 2008). Monocarboxylate transporter 1 inhibition is thus a potential anti-tumour strategy that would indirectly eradicate hypoxic/glycolytic tumour cells.

[figure not shown]

In many tissues, more than one MCT isoform is found which would appear to correlate with either the influx or efflux of lactic acid into different cell types. For example in skeletal muscle, the white fibres are glycolytic and contain primarily MCT4, the lactic acid effluxed by this transporter is then taken up and oxidised by the red fibres that express primarily MCT1. Similarly glial cells in the brain, which contains both MCT1 and MCT4, can export lactic acid to be oxidised by the neurons that contain MCT1 and MCT2. As AZD3965 is a selective and potent MCT1 inhibitor global MCT inhibition across all isoforms should not occur. It is therefore hypothesised that in normal cells, when MCT1 is inhibited, the presence of other MCTs will transport lactate out of the cells to maintain the body's normal homeostasis. Accordingly the presence of MCT4 has been validated as a resistance mechanism in tumour cells since introduction of MCT4 into a cell line expressing only MCT1 prevents both lactate accumulation and the inhibition of cell growth by MCT1 inhibitors. This is supported by cell panel data which shows that tumour cell lines that predominantly express MCT1 tend to be highly sensitive to AZD3965, whereas those that co-express MCT4 are far less sensitive or resistant.

2.2 Investigational medicinal product

2.2.1 Structure of AZD3965

[figure not shown]
Details of the physical and chemical characteristics of AZD3965 are provided in the investigator brochure.

2.2.2 Mechanism of action of AZD3965

The scientific rationale for the proposed trial is that many tumours have an increased dependency on the glycolytic pathway for ATP generation either via aerobic glycolysis or anaerobic glycolysis. Intracellular lactate produced by glycolysis is transported out of cells by the MCTs 1, 2, 3 and 4. Therefore by inhibiting MCT1, AZD3965 has the potential to inhibit the export of lactate from tumour cells, leading to lactate accumulation resulting in acidosis and cell death.

[figure not shown]
2.2.3 Non-clinical pharmacology

[figure not shown]

2.2.4 Safety pharmacology

2.2.5 Pharmacokinetics and metabolism

[figure not shown]

[figure not shown]
CRUKD/12/004 AZD3965 Protocol Version 14.0_FINAL_04Feb2020 EudraCT number: 2010-024463-41

[figure not shown]
2.2.6 Toxicology

[figure not shown]
- 2.2.7 Starting dose for Phase I and dose escalation considerations
- 2.2.7.1 MTD based approach

2.2.7.2 Predictive pharmacology based approach

2.2.8 Starting dose

2.2.9 Maximum Exposure

Based on the nature of adverse effects observed in non-clinical studies, dose escalation to maximum tolerated dose would not be appropriate for AZD3965 in man. Dose escalation could be stopped based on pharmacodynamic (PD) effects, e.g. PBMC lactate accumulation. However, there is limited clinical experience with the planned PD assays in this study, and these assays alone are not felt to be sufficient to inform dose escalation decisions with the appropriate degree of certainty. Instead an upper limit to the dose escalation of AZD3965 has been based on exposure levels.

In the CRUKD/12/004 trial, patients will undergo extensive clinical monitoring for potential retinal toxicity, which is expected to be reversible should it occur. A maximum AZD3965 exposure limit in humans is therefore set as a dose of AZD3965 producing a C_{max} not in excess of 5 µM and an AUC not in excess of 20 µmol•h/L. These levels of AZD3965 should allow dose escalation into the anticipated therapeutic range while remaining below the levels likely to affect retinal function. These levels may produce some QTc effects but these are likely to be minor and short-lived post-dosing. Based on extrapolation from nonclinical data, these exposure levels might be reached with a daily dose of around 500 mg/day.

Assessments of exposure will be based on Day -7, Day 1 and Day 29 pharmacokinetics from Part 1. If pharmacokinetics from any of these analyses indicate that the exposure cap has been exceeded the cohort will be completed (toxicity permitting) but no further dose escalations will take place. Pharmacokinetic data from all patients in a cohort must be available prior to dose escalation. If the drug demonstrates a good safety profile at doses producing exposures close to the planned cap a substantial amendment will be requested to allow further dose escalation.

2.3 Clinical experience

This is the first time an MCT-1 inhibitor will be given to humans.

[figure not shown]
2.4 Rationale for the proposed trial

AZD3965 is a first-in class agent in clinical development and this trial will be the first time AZD3965 will be administered in humans. Many tumours have an increased dependency on the glycolytic pathway for ATP generation either via aerobic glycolysis or anaerobic glycolysis. Intracellular lactate produced by glycolysis is transported out of cells by the MCTs 1, 2, 3 and 4. Therefore by inhibiting MCT1, AZD3965 has the potential to inhibit the export of lactate from tumour cells, leading to intracellular lactate accumulation resulting in lactic acidosis and cell death.

The first part of the trial followed a rolling six dose escalation schedule.

In addition, a dose of AZD3965 was given one week before the continuous treatment started to ensure patient safety.

In Part 2, up to 20 evaluable patients with relapsed or refractory diffuse large B cell Lymphoma (DLBCL) or Burkitt Lymphoma (BL) will be treated at the recommended phase II dose (RP2D) determined in Part 1. These tumour types were chosen based on AZD3965 activity that has been demonstrated in preclinical models of DLBCL and BL and on high MCT1 expression that has been reported in DLBCL and BL samples analysed by immunohistochemistry (IHC).

3 TRIAL DESIGN

In Part 1 each patient cohort included a maximum of six evaluable patients following a rolling six dose escalation scheme (Skolnik A.M. et al., 2008) of AZD3965 until a RP2D and/or the MTD was defined.

A total of 42 patients with advanced solid tumours were recruited into Part 1 of the study, 40 of whom received AZD3965.

A RP2D was proposed from the safety and PK results from Part 1.

All patients in Part 2 will receive AZD3965 at this RP2D to further explore the tolerability of this dose and schedule and to explore proof of principle of MCT1 inhibition in tumour types that are known to express high levels of MCT1 and low levels or no MCT4 which showed activity in pre-clinical models.

There will be up to 20 evaluable patients with relapsed or refractory DLBCL or BL entered into Part 2.

3.1 Clinical trial objectives and endpoints

3.1.1 Primary objectives and endpoints

Primary Objectives	Endpoints
1. To propose a RP2D of AZD3965 and/or the MTD in patients with advanced cancer, given via oral administration,	1. Determining a dose at which no more than one patient out of up to six patients at the same dose level experiences a highly probable or probably drug -related DLT and/or a biological effective dose based on PK and PD endpoints.
2. Establishing the safety profile of AZD3965,	2. Determining causality of each adverse event to AZD3965 and grading severity according to the NCI CTCAE version 4.02,

3.1.2 Secondary objectives and endpoints

Secondary Objectives	Endpoints
	1. Determining the plasma levels of AZD3965 after single and multiple doses of AZD3965,

•	2. Objective response: SD, PR, or CR according to RECIST, (version 1.1) or International Working Group criteria for Lymphoma (see Appendix 2A and 2B),
---	--

3.1.3 Tertiary objectives and endpoints

3.1.4 Definition of dose limiting toxicity

The DLT and MTD are defined using the NCI CTCAE Version 4.02.

Only DLTs identified during Part 1 Cycle 1 (including Day-7 in Part 1) informed the decision to dose escalate through the increasing dose levels. Dose limiting toxicities will be defined throughout the treatment period and will be considered in determining the RP2D for Part 2.

Any DLTs experienced during Part 2 will be collected to assist with assessment of adverse events (AEs) and patient safety profiles and the dose may be adjusted accordingly. Any changes to the Part 2 dose (RP2D) will be for safety reasons and to decrease the total daily dose only.

A DLT is defined as highly probably or probably drug related:

Haematological:

- neutropenia Grade 4 for \geq 5 days duration
- febrile neutropenia (fever of unknown origin without clinically or microbiologically documented infection) with Grade 3 or 4 neutropenia (absolute neutrophil count ANC <1.0x10⁹/L and fever ≥38.5°C)
- infection (documented clinically or microbiologically) with Grade 3 or 4 neutropenia (ANC <1.0x10⁹/L)

• thrombocytopenia Grade 4: a) for ≥5 days*, or b) associated with active bleeding, or c) requiring platelet transfusion.

Cardiac:

- QTc interval >500 msec or an increase of >60 msec from baseline (verified manually (Fridericia's correction (QTcF))
- Any other Grade 3 or 4 cardiac toxicity excluding Grade 3 hypertension
- Non-sustained ventricular tachycardia (<30s) associated with syncope or pre-syncope
- Sustained ventricular tachycardia (≥30s) with or without symptoms
- Ejection Fraction (EF): ≥20% reduction in left ventricular ejection fraction (LVEF) to below the lower limit of normal (<50% on echocardiography)

Ophthalmic:

Part 1:

- 25% (or more) reduction on electroretinography (light and dark adapted) which does not resolve to baseline or 25% (or less) within 2 weeks following dose delay
- 50% (or more) reduction on electroretinography (light and dark adapted)

Part 2:

- 25% (or more) a- wave reduction on electroretinography (light and dark adapted) which does not resolve to baseline or 25% (or less) within 2 weeks following dose delay
- 50% (or more) a wave reduction on electroretinography (light and dark adapted)
- 50% (or more) b- wave reduction on electroretinography (light and dark adapted) which does not resolve to baseline or 50% (or less) within 2 weeks following dose delay

*Note: If a patient is withdrawn from the study due to eye toxicity, ERG assessments will be repeated within 14 days and performed at least monthly thereafter until resolution or return to baseline. See Section 17.5 for further guidance.

Other

• Grade 3 or 4 toxicity to organs other than the bone marrow including Grade 3 and 4 biochemical AEs and DLTs

EXCLUDING:

- o Grade 3 nausea
- o Grade 3 vomiting in patients who have not received optimal treatment with anti-emetics
- \circ Grade 3 diarrhoea in patients who have not received optimal treatment with anti-diarrhoeals
- Death
- Any drug related toxicity that causes interruption of treatment for >2 weeks (14 successive days). If a patient is deemed fit to restart treatment on the fifteenth day then this is not a DLT.

* Note: In the event of a Grade 4 neutropenia or Grade 4 thrombocytopenia, a full blood count must be performed at least on Day 5 after the onset of the event to determine if a DLT has occurred. The Investigator must continue to monitor the patient closely until resolution to Grade 3 or less.

Should any change be made to the grade or causality of an AE during the trial that may alter its DLT status, the CDD must be informed immediately as this may affect dose escalation decisions.

PLEASE NOTE: In the event of an Ophthalmic and/or Cardiac DLT (as defined above) these must be reported as a serious adverse event (SAE) to the CDD (see Section 10 for guidance on SAE reporting).

3.1.5 Definition of maximum tolerated dose

In Part 1 if two out of up to six evaluable patients at the same dose level experienced a DLT as defined in Section 3.1.4, the MTD was determined as the total daily dose level below. The MTD, was used to determine the RP2D following discussion of all the relevant safety, PK and PD data between CDD and the Investigators.

3.2 Patient evaluability

Part 1:

All patients that met the eligibility criteria and take at least one dose of AZD3965 were evaluable for safety decisions.

[figure not shown]
Patients who received less than 75% of their first continuous treatment cycle (for reasons other than toxicity) would not be evaluable for dose escalation decisions. Patients who completed 75% of their first continuous treatment cycle but did not complete the end of Cycle 1 ERG and ophthalmology assessments could also not be evaluable for dose escalation decisions. This was discussed on a per patient basis between the Investigator, Chief Investigator (CI) and CDD.

Part 2:

All patients that meet the eligibility criteria and take at least one dose of AZD3965 will be evaluable for safety decisions.

All patients who meet the eligibility criteria and take at least 75% of their first continuous treatment cycle (28 days) of AZD3965 and have a baseline assessment of disease will be evaluable for response.

To be assigned a status of complete response (CR) or partial response (PR), changes in tumour measurements must be confirmed by repeat measurements performed no less than four weeks after the response criteria are met. To be assigned a status of stable disease (SD), follow-up measurements must have met the SD criteria at least once and at least six weeks after the initial dose of the IMP AZD3965 is given.

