5.5.3 Dose delays

In the event of toxicity, treatment should be delayed for up to two weeks until these toxicities have resolved to Grade ≤ 1 or returned to baseline. If there is no recovery after a two week delay, the patient should be withdrawn from the trial.

Intermittent dosing schedules may be explored based on observed toxicities, PK and PD data.

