5.7.1 Replacement of patients

In **Part 1**, patients were replaced if they fulfilled the following criteria and three evaluable patients had not yet been treated at the same dose level:

• Patients who miss more than 25% of their first AZD3965 cycle (for reasons other than drug related toxicity).

Patients who missed more than 50% of their first AZD3965 cycle due to toxicity which was not dose limiting were discussed between the CDD and CI and a decision will be taken on whether the patient should be replaced by another at the same dose level.

Patients could be replaced if they were unable to complete

as to whether to replace such a patient depended on the status of the other patients within that cohort ERG data already obtained at that dose level. This

decision was made by the CDD in consultation with the CI.

In **Part 2**, patients will be replaced in this phase if they fulfil the following criteria:

• Patients who miss more than 25% of their first AZD3965 cycle (for reasons other than drug related toxicity).

Patients who complete more than 75% of their first AZD3965 cycle (for reasons other than drug related toxicity) but fulfil one of the following additional criteria may also be replaced in Part 2. This will be discussed on a per patient basis between the Investigator, CI and CDD.

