11.3 Tumour response

All patients who meet the eligibility criteria and receive at least 75 % of their first cycle of trial medication and have a baseline assessment of disease will be evaluable for response. To be assigned a status of CR or PR, changes in tumour measurements must be confirmed by repeat measurements performed no less than four weeks after the response criteria are met. To be assigned a status of stable disease (SD), follow-up measurements must have met the SD criteria at least once and at least six weeks after the initial dose of the investigational medicinal product (IMP) AZD3965 is given.

Should rapid tumour progression occur before the completion of 4 weeks, the patient will be classified as having early progression (EP).

Tumour response should be classified as "not evaluable" (NE), only when it is not possible to classify it under another response category, for example, when baseline and/or follow-up assessment is not performed or not performed appropriately.

Expert reviewers appointed by CDD may undertake an independent review of all the Investigator's assessed objective responses (CR and PR). The expert reviewers will include at least one specialist who is not an Investigator in the trial. In case of disagreement between the Investigator's and the expert

reviewers' assessment, discussion will take place between the two parties in order to reach a consensus. However, if it is not forthcoming, the assessment of the expert reviewers will be retained in the clinical study report. The eCRF will reflect the Investigator's opinion.

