14.5 Anti-tumour activity

Documenting anti-tumour activity is a secondary objective of this trial. Patients must receive at least 75% of their first cycle of the trial medication to be evaluable for response. Objective responses, the best tumour response achieved by each patient while on trial and the time to progression will be presented in the data listings.

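### In Part 2, a patient who misses more than a quarter of Cycle 1 through drug-related toxicity is neither response-evaluable nor replaced, so the response denominator depends on the drug's own toxicity

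*Protocol*

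**What the plan says.** Four sections of the Protocol bear on this point.

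- **Evaluability.** Section 3.2 (Part 2) counts as evaluable for response "All patients who meet the eligibility criteria and take at least 75% of their first continuous treatment cycle (28 days) of AZD3965", provided that they also have a baseline disease assessment. Section 11.3 asks that patients "receive at least 75 % of their first cycle of trial medication", and 14.5 says "Patients must receive at least 75% of their first cycle of the trial medication to be evaluable for response". The reason for missed drug plays no part in any of them. For safety decisions, 3.2 needs only one dose.
- **Delay.** Under 5.5.3, in the event of toxicity, "treatment should be delayed for up to two weeks until these toxicities have resolved" to Grade 1 or below or to baseline. A patient who has not recovered after two weeks is withdrawn. Section 3.1.4 treats a drug-related interruption as dose limiting by duration only when it exceeds 14 successive days.
- **Replacement.** For Part 2, 5.7.1 states that "patients will be replaced in this phase if they fulfil the following criteria", and the criterion is "Patients who miss more than 25% of their first AZD3965 cycle (for reasons other than drug related toxicity").
- **Size and reporting.** Part 2 is to enter up to 20 evaluable patients (1.3, 3.3). Anti-tumour activity is a secondary objective, data are presented descriptively (14.1), and best response for each patient goes into the listings (14.5).

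**The concern.** The evaluability rule and the replacement rule use the same 25%/75% cut but treat the cause of the shortfall differently. The replacement rule exempts drug-related toxicity; the response rule does not. A patient can therefore start treatment, have a delay that the protocol allows, restart, be scanned at the end of Cycle 2, and still not count towards response, with nobody enrolled in that patient's place.

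The patients removed this way are selected by an effect of the drug. A response proportion calculated in the evaluable set would describe only patients who tolerated most of the first cycle, not those who were given the drug. In a cohort of about 20, one or two such patients visibly move the proportion. The statement of up to 20 evaluable patients also becomes ambiguous, because these patients are evaluable for safety but not for response.

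**Working it through.** Part 2 has no sample-size calculation, error rate or precision target to reproduce, so the check is a day count followed by an illustration.

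**Inputs from the Protocol.** Cycle length 28 days (1.4, 3.2); response-evaluable if at least 75% taken (3.2, 11.3, 14.5); replaced if more than 25% missed for reasons other than drug-related toxicity (5.7.1); permitted toxicity delay up to 14 days (5.5.3); up to 20 evaluable patients (3.3).

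**Day count.** Share taken = (28 − d)/28 for d missed days. The cut is 0.75 × 28 = 21 days taken, so 7 missed.

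| Days missed in Cycle 1 | Share taken | Response-evaluable? | Replaced if drug-related toxicity? |
|---|---|---|---|
| 7 | 21/28 = 75.0% | yes | no |
| 8 | 20/28 = 71.4% | no | no |
| 14 | 14/28 = 50.0% | no | no |

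The gap is therefore 8 to 14 missed days. With twice-daily dosing (56 doses), 14 missed doses leave 42/56 = 75.0% and 15 leave 41/56 = 73.2%, so the cut falls at practically the same point.

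**Conditions.**

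1. The toxicity must be drug-related. A delay for unrelated toxicity that costs more than 25% does lead to replacement.
2. At least 8 missed days must fall inside Cycle 1, so the interruption must start by Day 21 (Days 21 to 28 are 8 days).
3. The cycle stays at 28 days. No rule in the Protocol lengthens it for a delay.

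Patients withdrawn for drug-related toxicity before taking 75% of Cycle 1 fall into the same gap.

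**Size.** The Protocol gives no rate of such events, so the rate q is an assumption. For 20 treated patients, the expected number affected is 20q and the chance of at least one is 1 − (1 − q)^20.

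| Assumed q | Expected affected | Chance of at least one |
|---|---|---|
| 5% | 1 | 64% |
| 10% | 2 | 88% |
| 20% | 4 | 99% |

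**Effect on a response proportion.** Assume 4 responders among 20 treated and 3 patients in the gap. Intervals are exact 95%.

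- All 20 counted: 4/20 = 20% (6% to 44%).
- The 3 excluded, none a responder: 4/17 = 24% (7% to 50%).
- The 3 excluded, two of them responders: 2/17 = 12% (1% to 36%).

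The direction depends on who is delayed, which cannot be known in advance. All three intervals are wide and overlap heavily.

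**The case against.** The case for leaving the text alone has four parts, and much of it stands.

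- **No response is lost from the record.** Section 11.3.1 has the response category entered at every visit with a disease assessment, and 14.5 lists best response for each patient. Section 11.3 also reserves the not-evaluable category for responses that cannot be classified otherwise. A reader might infer that a confirmed response in a delayed patient disappears; it does not. What is affected is membership of the evaluable set, and so any proportion based on it.
- **Not replacing toxicity losses can be deliberate.** Safety is a primary objective and these patients remain safety-evaluable. That is a sound reason not to replace them, but not a reason to exclude them from response.
- **Twenty is a ceiling.** The Protocol says up to 20, so a smaller response set breaks no stated target. A reader might infer a guaranteed shortfall against plan; the wording does not support that. It does leave open which kind of evaluable is meant.
- **The magnitude is assumed.** At q = 2% the chance of any affected patient among 20 is only 33%. The endpoint is descriptive and no power figure is touched.

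Two further readings are tempting and should not be made.

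- Section 5.7.1 lets patients be replaced case by case under additional criteria: "Patients who complete more than 75% of their first AZD3965 cycle (for reasons other than drug related toxicity) but fulfil". A reader might infer that discretion then decides who is in the response set. Those criteria are not visible in the public text, and 3.2 already makes every patient who meets its conditions evaluable, without excluding replaced patients.
- The Part 1 rule in 3.2 exempts toxicity from its 75% cut, which might look like an inconsistency with Part 2. It governs evaluability for dose-escalation decisions, not response, so it is no precedent.

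**Conclusion.** The point holds in limited form. Sections 3.2, 11.3 and 14.5, read with 5.5.3 and 5.7.1, place a Part 2 patient who misses 8 to 14 days of Cycle 1 for drug-related toxicity, or who is withdrawn early for it, outside the response-evaluable set and without a replacement. This follows from the text and a day count and needs no assumption beyond a fixed 28-day cycle.

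How often it happens is not known from the documents. On an assumed rate of 5% to 20%, it affects an expected 1 to 4 of 20 patients, enough to move an observed proportion by several percentage points in either direction. Because the endpoint is secondary and descriptive and the individual responses are listed, this is a definition that should be corrected, not a threat to the trial's primary conclusions. An unseen analysis plan may add a tabulation in all treated patients, but the exclusion itself is fixed in the Protocol.

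**What to change.** In 3.2, 11.3 and 14.5, add for Part 2: patients who receive less than 75% of Cycle 1 because of drug-related toxicity remain evaluable for response and are counted by their best response, or as non-responders if none is documented. In 1.3 and 3.3, state whether up to 20 evaluable means evaluable for safety or for response.

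Section 5.7.1 can stay as it is, since patients who remain evaluable need no replacement. No dosing, delay or withdrawal rule changes, and no new data are needed, because response is already recorded at each disease assessment. The cost is a wording amendment and a reported response rate that may be slightly less favourable, since patients withdrawn early for toxicity would mostly enter as non-responders.
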